**A NON-RANDOMIZED, CONSECUTIVE ENROLLMENT EVALUATION OF THE
DESolve® NOVOLIMUS ELUTING BIORESORBABLE CORONARY SCAFFOLD
SYSTEM IN THE TREATMENT OF PATIENTS WITH *DE NOVO* NATIVE
CORONARY ARTERY LESIONS**

**Elixir Medical Clinical Evaluation of the DESolve® Novolimus Eluting Bioresorbable
Coronary Scaffold System**

“DESolve Nx Trial – DESolve CX Arm”

Revision E, 5 February 2018

Brazil

NCT04034121

CLINICAL STUDY SUMMARY

Trial Name and Number	DESolve Nx Trial: ELX-CL-1003
Objectives:	To evaluate the safety, performance and efficacy of the Elixir DESolve [®] Novolimus Eluting Bioresorbable Coronary Scaffold System (BCSS) in patients with a single de novo native coronary artery lesion designated the target lesion and up to one non-target lesion located in a separate epicardial vessel.
Enrollment:	The study is designed to enroll 120 non-randomized patients with a single de novo native coronary artery lesion designated the target lesion and up to one non-target lesion located in a separate epicardial vessel. The target lesion must measure between 2.75 mm and 3.5 mm in diameter and ≤ 10 mm or ≤ 14 mm in length able to be covered by a single 3.0 x 14, 3.0 x 18mm, 3.25 x 14 or 3.25 x 18 mm, 3.5 x 14 mm or 3.5 x 18 mm DESolve scaffold. As applicable, a non-target lesion located in a separate epicardial vessel must be treated first with a single, approved ‘olimus drug eluting stent and if this procedure is uncomplicated and considered optimal, then the target lesion can be considered for the DESolve Novolimus Eluting BCSS. The patient should not be enrolled until after satisfactory pre-dilatation of the target lesion. Enrollment and follow-up is complete.

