	The Low Profile 1 study arm is designed to enroll 100 non-randomized patients with a single de novo native coronary artery lesion designated the target lesion and up to one non-target lesion located in a separate epicardial vessel. The target lesion must measure between 2.75 mm and 3.5 mm in diameter and ≤ 10 mm or ≤ 24 mm in length able to be covered by a single 3.0, 3.25 or 3.5 mm x 14, 18 or 28 mm scaffold. This device differs only in the thickness of the scaffold which is now 100-120 μm as compared to the 150 μm of the device previously studied and shown safe and effective. As applicable, a non-target lesion located in a separate epicardial vessel must be treated first with a single, approved ‘olimus drug eluting stent and if this procedure is uncomplicated and considered optimal, then the target lesion can be considered for the DESolve Novolimus Eluting BCSS. The patient should not be enrolled until after satisfactory pre-dilatation of the target lesion. Patients included in this

	Arm will be enrolled at select sites. Follow-up will conclude at the end of 3 years.
Clinical Study Device	
3.0 x 14 mm, 3.0 x 18 mm, and 3.0 x 28mm; 3.25 x 14 mm, 3.25 x 18 mm and 3.25 x 28 mm; 3.5 x 14mm, 3.5 x 18 mm and 3.5 x 28 mm DESolve scaffolds
 
All DESolve scaffolds are loaded with approximately 5 mcg of Novolimus per mm of scaffold length (i.e, 65 mcg on a 14 mm scaffold, 85 mcg on an 18 mm scaffold and 125 mcg on a 28 mm scaffold).

Clinical Site Locations:	Drawn from up to 15 International Sites in Brazil, Belgium, Denmark, Germany, Poland and New Zealand

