Clinical Endpoints:	
 • Clinically-indicated Major Adverse Cardiac Events (MACE) at 1, 6, and 12 months and annually to 5 years for all main study patients and for Low Profile 1 (LP1) patients at 1, 6, and 12 months and annually through 3 years. MACE is a composite endpoint defined as cardiac death, target vessel MI, and clinically-indicated target lesion revascularization • Acute Success including Device and Procedure Success • Clinically-indicated Target Lesion and Target Vessel Revascularization (CI-TLR and CI-TVR) at 1, 6, and 12 months and annually to 5 years for all main study patients and for LP1 patients at 1, 6, and 12 months and annually through 3 years • Clinically-indicated Target Lesion and Target Vessel Failure (CI-TLF and CI-TVF) at 1, 6, and 12 months and annually to 5 years for all main study patients and for LP1 patients at 1, 6, and 12 months and annually through 3 years • Scaffold Thrombosis at 1, 6, and 12 months and annually to 5 years for all main study patients and for LP1 patients at 1, 6, and 12 months and annually through 3 years
Angiographic Endpoints:	
All patients will undergo angiographic follow-up at 6 months. In a subset of the first 35 patients enrolled at select sites angiography will also be conducted at 24 and/or 36 months.
 
The following endpoints will be analyzed:
 
 • In-scaffold late lumen loss • In-scaffold and in-lesion Binary Restenosis ($\geq 50\%$) • In-lesion Late Lumen Loss

	
 • In-scaffold and in-segment % Diameter Stenosis • MLD and % DS post procedure • Scaffold Thrombosis • Additional parameters may be assessed
IVUS and OCT Endpoints	
To provide an assessment of the lesion and stent morphology and stent strut composition over time, the additional imaging modalities of IVUS and OCT conducted at baseline, 6 and 24 and/or 36 months will be completed in a subset of the first 35 patients enrolled at select sites. The following endpoints will be analyzed:
 
 • Volumetric neointimal burden by IVUS • Changes in vessel size by IVUS • Changes in scaffold size by IVUS • Changes in strut appearance suggesting bioresorption • Incomplete scaffold apposition, acute and late, assessed by IVUS and/or Optical Coherence Tomography (OCT) • Scaffold area assessed by IVUS and/or OCT • Descriptive analysis of lesion/vessel morphometry and scaffold strut composition by OCT

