
Key Exclusion Criteria
	
Patients must not have any of the following:
 
 • An untreated significant lesion of > 40% diameter stenosis remaining proximal or distal to the target site after the planned intervention • The lesion is aorto-ostial in location, an unprotected left main lesion, a lesion within 5 mm of the origin of the LAD or LCX, or involves a major side branch < 2mm in diameter • Previous placement of a stent proximal to or within 10 mm of the target lesion • Total occlusion or < TIMI 1 coronary flow in the target vessel • The proximal target vessel or target lesion contains thrombus, moderate to severe calcification or exhibits severe tortuosity ($\geq 45^\circ$ angulation) by visual assessment • High probability that treatment other than PTCA or stenting will be required for treatment of the same lesion • Patient is a woman of childbearing potential, pregnant or nursing • Patient has received brachytherapy in an epicardial vessel • Any use of rotablator at the index procedure • The patient was diagnosed with an acute myocardial infarction (AMI) within the past 72 hours and the CK and CKMB have not returned to normal and the patient is experiencing clinical symptoms indicative of ongoing ischemia

Statistical Analysis
	
Analysis Populations in this observational study.
 
Modified-Intent-to-Treat Evaluable Population
 
The modified-intent-to-treat evaluable population will consist of patients who have received the investigational device at the target lesion, who have no major procedural protocol deviations (e.g. scaffold implanted in a non-native coronary artery), no bailout scaffolding and for whom follow-up data is available.

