	
Intent-to-Treat Population
 
The intent-to-treat population will consist of all patients enrolled in the study, regardless of the treatment actually received for the target lesion.
 
Statistical Analyses
 
Detailed descriptive analyses of endpoints will be performed after each follow-up time point. No effort will be made to impute or extrapolate data to replace missing values. All calculations will be based on available data with missing data excluded. Any unused or spurious data will be noted as appropriate in the final report.
 
All clinical, angiographic, IVUS and OCT endpoints will be analyzed for the modified-intent-to-treat evaluable population. Descriptive statistics will be presented.
 
For binary variables such as MACE, ABR, TLR, TVF, and persistent incomplete apposition of the scaffold, counts, percentages, and exact 95% confidence intervals using Clopper-Pearson’s method will be calculated.
 
For continuous variables, means, standard deviations, and 95% confidence intervals for the mean using the Gaussian approximation will be calculated. If the assumption of normality seems untenable, nonparametric summary statistics will be presented instead.
 
For time-to-event variables, such as time to TVF, survival curves will be constructed using Kaplan-Meier estimates.

--	---

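### All clinical endpoints, including Acute Success, are assigned to an evaluable set that excludes patients for events after enrolment, and the all-enrolled set is given no analysis

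*Protocol*

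**What the plan says.** All references are to the Clinical Study Summary in the protocol.

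- **Analysis set.** Under Statistical Analyses: "All clinical, angiographic, IVUS and OCT endpoints will be analyzed for the modified-intent-to-treat evaluable population".
- **Who is in that set.** Patients must have received the investigational device at the target lesion, have had no major procedural protocol deviation, "no bailout scaffolding and for whom follow-up data is available".
- **The other set.** "The intent-to-treat population will consist of all patients enrolled in the study, regardless of the treatment actually received for the target lesion". No later sentence in the text assigns this set an analysis.
- **Which endpoints are clinical.** The Clinical Endpoints row lists "Acute Success including Device and Procedure Success" with MACE, clinically indicated target lesion and target vessel revascularization (TLR/TVR), target lesion and target vessel failure (TLF/TVF), and scaffold thrombosis.
- **When a patient is enrolled.** The Enrollment row says, for both cohorts: "The patient should not be enrolled until after satisfactory pre-dilatation of the target lesion".
- **Missing data.** "All calculations will be based on available data with missing data excluded". Nothing is imputed, and Kaplan-Meier curves are planned for time-to-event variables. On data left out: "Any unused or spurious data will be noted as appropriate in the final report".
- **Status.** For the 120-patient main study: "Enrollment and follow-up is complete". The 100-patient Low Profile 1 arm is described in the future tense.

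**The concern.** Each condition for entering the evaluable set becomes known during or after the index procedure, while enrolment is fixed before the scaffold is placed. Membership therefore depends partly on how the procedure went.

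This is nearly circular for Acute Success. The endpoint is meant to show how often the device is delivered successfully, yet it would be computed only among patients who received the device and, on the natural reading, needed no bailout.

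For MACE, revascularization, target lesion or vessel failure and scaffold thrombosis, the rates and exact intervals would describe a group selected by procedural course and completeness of follow-up. There is no control arm subject to the same selection. The analysis is purely descriptive, so these rates and intervals are the study's main output, and their denominator determines what they mean.

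**Working it through.** **Does the plan do this?** Read together, the rows say the following.

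1. Enrolment follows satisfactory pre-dilatation and precedes scaffold placement (Enrollment).
2. Device receipt, procedural deviations, bailout and follow-up are all determined later (Modified-Intent-to-Treat Evaluable Population).
3. Bailout is foreseen (Treatment Strategy), so that exclusion can take effect.
4. Acute Success is a clinical endpoint, and all clinical endpoints go to the evaluable set (Clinical Endpoints; Statistical Analyses).
5. The all-enrolled set is defined but not used. Noting unused data in the report does not produce an all-enrolled rate.
6. The follow-up condition is not needed to deal with missing data. The available-data rule and Kaplan-Meier estimation both work on the ITT set without imputation.

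**Which way does Acute Success move?** Let N be the number enrolled, F the acute failures, f the failures excluded from the evaluable set, and m the successes excluded from it (for example, for lack of follow-up).

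- ITT rate = (N − F)/N
- Evaluable rate = (N − F − m)/(N − f − m)
- The evaluable rate is the higher one if and only if f/(f + m) > F/N, that is, if the failure share among the excluded exceeds the failure share among all enrolled.
- Break-even: m = f(N − F)/F

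**Inputs.** N = 100 (Low Profile 1) and N = 120 (main study) are from the protocol. The values of F, f and m are assumed, because the protocol gives no failure, bailout or deviation rate. Device and Procedure Success are not defined in the text, so it is also an assumption that failed delivery or bailout counts as a failure. Intervals are Clopper-Pearson 95%, the protocol's own method.

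| N | F | f | m | ITT | Evaluable set |
|---|---|---|---|---|---|
| 100 | 5 | 5 | 0 | 95/100 = 95.0% (88.7–98.4) | 95/95 = 100% (96.2–100) |
| 100 | 8 | 5 | 0 | 92/100 = 92.0% (84.8–96.5) | 92/95 = 96.8% (91.0–99.3) |
| 100 | 8 | 5 | 20 | 92/100 = 92.0% (84.8–96.5) | 72/75 = 96.0% (88.8–99.2) |
| 100 | 10 | 1 | 20 | 90/100 = 90.0% (82.4–95.1) | 70/79 = 88.6% (79.5–94.7) |
| 120 | 6 | 6 | 0 | 114/120 = 95.0% (89.4–98.1) | 114/114 = 100% (96.8–100) |

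Break-even values:

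- N = 100, F = 8, f = 5: 5 × 92/8 = 57.5. The sign reverses only with more than 57 excluded successes.
- N = 100, F = 10, f = 1: 1 × 90/10 = 9. With 9 excluded successes both rates are 90.0% (81/90). With 20 the evaluable rate is the lower one, as in the fourth row.
- N = 100, F = 5, f = 5: 5 × 95/5 = 95, which is every success. If all failures are excluded, the evaluable set shows 100% however many there were.

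**MACE, direction only.** Take N = 120, five patients excluded and five events among the 115 kept (assumed). If two of the excluded patients also had an event, the evaluable rate is 5/115 = 4.3% against 7/120 = 5.8% on ITT. If none did, it is 4.3% against 5/120 = 4.2%. The sign depends on outcomes the plan would not tabulate, so no size is claimed.

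**The case against.** **The all-enrolled set may be used elsewhere.** The text does not say that only the evaluable set will be analysed, and a statistical analysis plan that is not shown may add ITT tables. This stands as a caution: the silence on ITT would carry little weight alone. But the protocol positively names a different set for all clinical endpoints, and that sentence is the defect.

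**The bailout exclusion is uncertain.** The population definition speaks of bailout scaffolding, while Treatment Strategy speaks of bailout stenting with an approved drug-eluting or bare metal stent. Read literally, a patient given the study scaffold and then a metallic stent might stay in. If so, fewer failures leave and the all-excluded rows become less plausible. Failed deliveries still leave, because non-receipt of the device alone excludes them.

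**The follow-up condition can be read per endpoint and visit.** It would then remove nobody from Acute Success. The rows with 20 excluded successes need the whole-study reading. The other rows do not.

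**The counts have no anchor.** This is correct. Screening before enrolment (satisfactory pre-dilatation, no dissection worse than Type A) may keep failures rare. With one excluded failure in 100, the contrast is 99/100 = 99.0% against 99/99 = 100%.

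**No decision turns on it.** The study is observational, with no stated hypothesis or success criterion, so neither type I error nor power is at issue. This limits the severity but does not make the rates correct. An evaluable set is a fair way to describe an implanted device's performance; the fault is naming it alone for clinical endpoints.

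**Making ITT the main set for Low Profile 1 could also be after the fact.** Its data status at Revision E is not stated outright. Its enrolment and follow-up are written in the future tense, however, so nothing in the text shows the change would come late.

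**Conclusion.** The concern holds and should be fixed. As written, the plan computes every clinical endpoint, Acute Success included, in patients selected by events after enrolment, and leaves its own all-enrolled set without an analysis.

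Acute Success is likely, though not certain, to be overstated. That rests on two assumptions: failed delivery or bailout counts as a failure, and failures are over-represented among the excluded. The illustrated overstatement runs from one percentage point (one excluded failure in 100) to five points (five of 100, or six of 120), and the sign can reverse if few failures but many successes are excluded. For MACE, TLR/TVR, TLF/TVF and scaffold thrombosis, the rates describe a selected group and the direction of bias is unknown.

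Confidence in the defect is high. Its size cannot be known from the protocol.

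**What to change.** In the Statistical Analyses text:

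1. **Low Profile 1 arm.** Make the already defined ITT set the main set for Acute Success, MACE, TLR/TVR and TLF/TVF, using the available-data and Kaplan-Meier rules already stated.
2. **Main study.** Because it is complete, report ITT alongside the evaluable set and do not replace the planned set after the fact.
3. **Scaffold thrombosis.** Report it in all patients who received a study scaffold, including those with bailout or deviations, alongside ITT.
4. **Evaluable set.** Keep it as supportive for the clinical endpoints and as the set for the angiographic, IVUS and OCT endpoints.
5. **Exclusions.** List every patient left out of the evaluable set, with the reason and any events.
6. **Wording.** Use one term for bailout in Treatment Strategy and in the population definition. State that a death or other event before the first visit counts as follow-up data.

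The cost is a wording change, one rerun of existing tables and a short listing, with no new patients or visits. The reported rates may become less favourable.

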Clinical Study Design	
The DESolve Nx Trial is a prospective, consecutive enrolment non-randomized study designed to enroll patients with a de novo lesion \leq 14 mm in length, designated the target lesion, located in a native coronary artery with a reference vessel diameter of 2.75 mm – 3.5 mm. All patients will receive a 3.0, 3.25 or 3.5 mm x 14, 18 or 28 mm scaffold. DESolve scaffold loaded with approximately 5 mcg of Novolimus per mm of scaffold length. As appropriate, a non-target lesion may be treated in a separate native epicardial vessel with a single, approved ‘olimus drug eluting stent. Only the target vessel will be evaluated for the key safety and efficacy endpoints.
 
Multiple registry arms are to be included in the study with patients to be enrolled at select sites:
 
 • Low Profile 1 – a lower profile (thinner) scaffold (100-120μm) with the same drug dose 
To provide an assessment of the lesion and scaffold morphology and scaffold strut composition over time, the following additional imaging modalities will be included:
 
 • Angiography will be completed at 6 months following the index procedure in all patients. • In a subset of the first 35 patients enrolled at select sites, IVUS and OCT will be conducted at 6 and 24 and/or 36 months following the index procedure. These patients will also undergo angiography during the 24 and/or 36 month follow-up.

	
 • Multislice computed tomography (MSCT) will be conducted at 12 months in the subset of the first 35 patients enrolled at select sites. • All main trial patients will undergo clinical follow-up at 1, 6, and 12 months and annually through 5 years. • LP1 patients will undergo clinical follow-up at 1, 6, and 12 months and annually through 3 years

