MSCT Analysis Endpoint	
In a subset of the first 35 patients enrolled at select sites, MSCT follow-up will be conducted at 12 months. The following endpoints will be analyzed:
 
 • Multi-slice computed tomography (MSCT) descriptive and quantitative analysis of lesion/vessel and scaffold morphology
Treatment Strategy	
 • Treatment of up to two de novo native coronary artery lesions located in separate epicardial territories. One will be the target lesion and will be treated with the trial device.

- Treatment of the target lesion is to be performed after optimal stenting using an approved 'olimus DES of a single non-target lesion as applicable.
- To determine patient eligibility, assessment of the target vessel diameter using on-line QCA must be completed before the enrollment of the patient into the study. The target lesion is to be treated only after all clinical and angiographic inclusion criteria have been met
- Pre-dilatation of the lesion is mandatory using a balloon approximately sized to the reference vessel. If the lesion cannot be successfully pre-dilated, treatment with the DESolve CSS should not be attempted. If there is Type A dissection that cannot be covered by the DESolve CSS then the patient cannot be enrolled in the trial. Any dissection worse than Type A will preclude the patient from being enrolled into the study.
- Target lesion length should be ≤ 10 mm or ≤ 24 mm by visual estimate and have at least 2 mm of healthy vessel on either side of the lesion for coverage by the DESolve Scaffold

Table 1: Lesion length, Scaffold size and Drug dose

Lesion length (visual estimation)	DESolve Stent size	Drug dose
≤ 10 mm	3.0 x 14 mm	65 mcg
	3.25 x 14 mm	
	3.5 x 14 mm	
≤ 14 mm	3.0 x 18 mm	85 mcg
	3.25 x 18 mm	
	3.5 x 18 mm	
≤ 24 mm	3.0 x 28 mm	125 mcg
	3.25 x 28 mm	
	3.5 x 28 mm	

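### Confidence intervals for means, read as mean ± 1.96 SE, would be slightly too narrow in the imaging subset of at most 35 patients

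*Protocol*

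**What the plan says.** The Statistical Analyses section of the protocol summary plans means, standard deviations and "95% confidence intervals for the mean using the Gaussian approximation will be calculated" for continuous variables. The next sentence gives a fallback: "If the assumption of normality seems untenable, nonparametric summary statistics will be presented instead". For binary variables, the paragraph before specifies exact Clopper-Pearson intervals. No z or t quantile is named for means.

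The sample sizes behind these intervals differ widely:

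- **Main study (Enrollment):** "The study is designed to enroll 120 non-randomized patients".
- **Low Profile 1 arm (Enrollment):** "The Low Profile 1 study arm is designed to enroll 100 non-randomized patients".
- **IVUS and OCT (Clinical Study Design):** "In a subset of the first 35 patients enrolled at select sites, IVUS and OCT will be conducted", at 6 months and then at 24 months, 36 months or both. The same patients have the late angiography.
- **MSCT (MSCT Analysis Endpoint):** "In a subset of the first 35 patients enrolled at select sites, MSCT follow-up will be conducted at 12 months".

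Angiography at 6 months is planned for all patients. On missing values the protocol says: "All calculations will be based on available data with missing data excluded".

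**The concern.** When the standard deviation is estimated from the same sample, the standardised mean follows a t distribution under normality, not a Gaussian one. An interval built with 1.96 then leaves out the uncertainty in the standard deviation and covers less than its label says. The gap is trivial in large samples and grows as the sample shrinks.

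The gap matters most here for the serial imaging means, such as neointimal burden and changes in vessel and scaffold size by IVUS. Thirty-five patients is a ceiling for these. Missing data are excluded. The modified-intent-to-treat evaluable population also drops patients with bailout, major procedural deviations or no follow-up data. Late imaging may be divided between two visits. In a descriptive study the estimates and their intervals are the result, so an interval labelled 95% should have that coverage.

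**Working it through.** **Inputs from the protocol.** Two-sided 95% intervals for means (Statistical Analyses); an imaging subset of at most 35 (Clinical Study Design, IVUS and OCT Endpoints, MSCT Analysis Endpoint); 120 patients in the main study and 100 in the Low Profile 1 arm (Enrollment).

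**Assumed inputs.** Analysed numbers of 20 and 17. The protocol gives no attrition rate and no division of patients between 24 and 36 months. Seventeen is about half of 35; 20 is an intermediate case. No standard deviation is needed, because the coverage and the ratio of widths depend only on n.

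**Formulas**, for approximately normal data:

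- Interval: mean ± q × SD/√n, with q = 1.960 (Gaussian) or q = t(0.975, n−1).
- True coverage of the Gaussian interval: 2·T(1.960) − 1, where T is the t distribution function with n−1 degrees of freedom.
- Relative width of the t interval: t(0.975, n−1)/1.960.

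**The protocol's own figure.** The only stated figure is the nominal 95%. The t quantile reproduces it exactly at every n under normality. The Gaussian quantile does not.

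**At n = 35:**

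- t(0.975, 34) = 2.032, and 2.032/1.960 = 1.037, so the t interval is 3.7% wider.
- Half-widths: 1.960/√35 = 0.331 SD (Gaussian) and 2.032/√35 = 0.344 SD (t).
- Coverage of the Gaussian interval: 94.2%.

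**Across sizes:**

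| n | Source | t quantile | t interval wider by | Coverage with 1.960 |
|---|---|---|---|---|
| 120 | protocol | 1.980 | 1.0% | 94.8% |
| 100 | protocol | 1.984 | 1.2% | 94.7% |
| 35 | protocol, upper bound | 2.032 | 3.7% | 94.2% |
| 20 | assumed | 2.093 | 6.8% | 93.5% |
| 17 | assumed | 2.120 | 8.2% | 93.2% |

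The Gaussian interval is the narrower one at every n, so the discrepancy always runs towards overstating precision.

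**The case against.** **The quantile is not named.** The fallback sentence speaks of an assumption of normality, so the phrase could mean a normal-theory interval with a t quantile, which has exact coverage. This stands to the extent that under-coverage cannot be stated as fact. A t interval would not ordinarily be called an approximation, though, and the exact binary intervals in the preceding paragraph suggest a deliberate contrast. If the wording allows both readings, it does not determine the interval, and the same edit settles it.

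**The choice belongs in a SAP.** A protocol may leave the quantile to the SAP. This one does not stay silent: it names a method for means, and a better one costs nothing.

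**The effect is small and nothing depends on it.** This is correct. No test, margin or success criterion rests on an interval for a mean. The means and standard deviations are unaffected, so a reader who knows n can rebuild the interval. Several subset endpoints are not means at all: strut appearance and the OCT morphology are descriptive, and persistent incomplete apposition is binary with an exact interval.

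**Stronger readings a reader might infer.** One is that coverage falls much further because imaging measurements are often skewed. The protocol does not support this, since clearly non-normal data are sent to nonparametric summaries. Another is that the narrower intervals favour the device. There is no threshold for them to favour.

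**Conclusion.** The point holds as a minor correction. On the natural reading of the Statistical Analyses section, 95% intervals for means in the imaging subset have true coverage of 94.2% at the maximum of 35 patients, and the t interval would be 3.7% wider. Coverage would be about 93.5% or 93.2% if only 20 or 17 patients were analysed. For endpoints measured in 100 to 120 patients, including 6-month late lumen loss, the difference is about 1% and negligible.

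This rests on three assumptions: that the Gaussian approximation means the 1.960 multiplier with an estimated standard deviation; that the data are close enough to normal for the fallback not to apply; and, below 35, on sample sizes the protocol does not give. No conclusion of the study would reverse. The consequence is limited to slightly overstated precision for the continuous imaging endpoints.

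**What to change.** In the Statistical Analyses section, replace the Gaussian approximation by *the Student t distribution with n−1 degrees of freedom* for all intervals for means, and keep the nonparametric fallback as written. Reporting the analysed n beside each interval would let readers see where the subset has shrunk.

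The change costs a few words and needs no further data. Intervals become about 1% wider with 100 to 120 patients and 3.7% wider with 35, and more than that if fewer patients are analysed.
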